Initial RP2D of MS-553 for the combination is expected to be reached before the dose escalation reaches 250 mg BID, the high dose level of MS-553 under testing as monotherapy. Intermediate dose levels (i.e. at 25 mg increment) or even lower dose levels may also be evaluated as determined by the Investigators, the Safety Review Committee and Sponsor until the MTD or initial RP2D for the combination is determined.

Cohort C2. After the MTD or initial RP2D is identified for the combination of MS-553, venetoclax and rituximab, an expansion cohort of approximately 20 patients will be initiated. Treatment experienced CLL/SLL patients, eligible for standard of care venetoclax and rituximab, who are naïve to prior Bcl-2 inhibitor treatment and who have had no more than 2 prior lines of treatment regimens are eligible for this cohort to further confirm the safety of the combination and assess early evidence of anti-tumor activity. Venetoclax will be initiated on Cycle 3 following the administration of MS-553 and rituximab combination for two cycles. For this reason, the DLT evaluation period for the triplet combination is extended to 4 cycles of therapy in order to include ramping up of the venetoclax dose that is introduced in Cycle 3.

Patients in Cohort C1 and C2

Patients will be treated in 28-day cycles provided they continue to tolerate the drug, have no evidence of progression, and do not meet any of the criteria for discontinuation. All patients will continue to be monitored for approximately 30 days (+7 days) after treatment discontinuation for development of any late treatment emergent adverse events. Any adverse events noted during the DLT evaluation periods will be considered in the determination of the maximum tolerated dose/initial RP2D and dose schedule to be taken forward into the expansion phase of the study.

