In Cohort C1, at least 3 patients will be enrolled at starting dose level of 150 mg BID. The dosing rules for Cohorts A1 and B1 will be similarly applied to Cohort C1. For the dose levels of MS-553 up to and including 225 mg BID, the DLT evaluation period will be through Cycle 4 (16 weeks). During the DLT evaluation period, if \leq 1 DLT is observed, then escalation to the next higher dose level will follow the 3+3 design and proceed when 3/3 or 5/6 patients have completed four treatment cycles without a DLT. If at least 1 of 3 patients experiences a DLT at any dose level, the cohort will be expanded to 6 patients. If \geq 2/3 or \geq 2/6 patients experience a DLT within a cohort, the MTD will be considered to have been exceeded. At Sponsor discretion, additional patients may be enrolled into a cohort where \leq 1 patient develops a DLT to obtain additional safety, PK, PD, and/or efficacy data.

Determination of DLT for dosing Cohorts A1

Each dose cohort will include a minimum of 3 evaluable patients for assessment of DLT. In order to be considered evaluable for DLT, patients must meet at least one of the following criteria:

- 1. Complete one 28-day cycle and receive at least 75% of MS-553 intended doses in Cycle 1
- 2. Discontinue due to DLT

During the DLT evaluation period for each cohort, non-evaluable patients who discontinue treatment before one cycle is complete for reasons other than study drug-related toxicities (e.g., progressive disease, non-compliance), or do not receive at least 75% of MS-553 doses, will be replaced with additional patients enrolled at the same dose level. After a DLT is resolved or reversed to \leq Grade 1, the study drug may continue at a lower dose level at the discretion of the investigator.

A decision on dose escalation to the next dose level will be based on evaluation of the clinical safety profile and may also include evaluation of MS-553 exposure in treated patients. After the completion of each cohort, safety and PK data (if available) will be

reviewed and a decision on dose escalation will be determined by the Investigators, the Safety Review Committee, and the Sponsor.

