After completion of each dose escalation cohort, the Safety Review Committee (SRC) will review clinical safety and tolerability data as well as PK data available at the time for all patients in order to confirm dose escalation to the next dose level. Based on the SRC's review, a cohort may be expanded, or an intermediate or a lower-than-planned dose level or an alternative dosing schedule may be evaluated.

Determination of DLT for dosing Cohort B1

Each dose cohort will include a minimum of 3 evaluable patients for assessment of DLT. In order to be considered evaluable for DLT, patients must meet at least one of the following criteria:

- 1. Complete one 28-day cycle and receive at least 75% of MS-553 intended doses in Cycle 1;
- 2. Discontinue due to DLT

During the DLT evaluation period for each cohort, non-evaluable patients who discontinue treatment before the DLT evaluation period is complete for reasons other than study drug-related toxicities (e.g., progressive disease, non-compliance), or do not receive at least 75% of MS-553 doses, will be replaced with additional patients enrolled at the same dose level. After a DLT is resolved or improved to \leq Grade 1, the study drug may continue at a lower dose level at the discretion of the investigator.

A decision on dose escalation to the next dose level will be based on evaluation of the clinical safety profile and may also include evaluation of MS-553 exposure in treated patients. After the completion of each cohort, safety and PK data (if available) will be reviewed and a decision on dose escalation will be determined by the Investigators, the Safety Review Committee, and the Sponsor.

After completion of each dose escalation cohort, the SRC will review clinical safety and tolerability data as well as PK data available at the time for all patients in order to confirm dose escalation to the next dose level. Based on the SRC's review, a cohort may be expanded, or an intermediate (i.e., at 25 mg increment) or a lower-than-planned dose level or an alternative dosing schedule may be evaluated.

Determination of DLT for dosing Cohort C1

Each dose cohort will include a minimum of 3 evaluable patients for assessment of DLT. In order to be considered evaluable for DLT, patients must meet at least one of the following criteria:

- 1. Complete the first four consecutive 28-day cycles and receive at least 75% of MS-553 intended doses in these cycles
- 2. Discontinue due to DLT

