During the DLT evaluation periods for Cohort C1, non-evaluable patients who discontinue treatment before the DLT evaluation periods are complete for reasons other than study drug-related toxicities (e.g., progressive disease, non-compliance), or do not receive at least 75% of MS-553 doses, will be replaced with additional patients enrolled at the same dose level. After a DLT is resolved or reversed to \leq Grade 1, the study drug may continue at a lower dose level at the discretion of the investigator.

A decision on dose escalation to the next dose level will be based on evaluation of the clinical safety profile and may also include evaluation of MS-553 exposure in treated patients. After the completion of each cohort, safety and PK data (if available) will be reviewed and a decision on dose escalation will be determined by the Investigators, the SRC, and the Sponsor.

After completion of each dose escalation cohort, the SRC will review clinical safety and tolerability data as well as PK data available at that time for all patients to confirm dose escalation to the next dose level. Based on the SRC's review, a cohort may be expanded, or an intermediate (i.e., at 25 mg increment) or a lower-than-planned dose level or an alternative dosing schedule may be evaluated.

Safety

For Cohort A1, assessments for DLT and TEAE will occur during Cycle 1. For Cohort B1, assessments for DLT and TEAE will occur during Cycle 1 for dose levels up to and potentially including 225 mg BID. For Cohort C1, assessments for DLT and TEAE will occur from Cycle 1 through Cycle 4 for dose levels up to and potentially including 225 mg BID. TEAE will be assessed during the course of the trial. The primary safety endpoint will be the rate of DLT and TEAE requiring study drug discontinuation in the DLT evaluable period.

Toxicities will be defined using NCI CTCAE v5.0 criteria.

Efficacy

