3.3.2. Dose Escalation: General Principles

During the first cycle of any dose level, if ≤ 1 Dose Limiting Toxicity (DLT; as defined in Section 3.3.1) is observed, then escalation to the next higher dose level will follow the 3+3 design and proceed when 3/3 or 5/6 patients have completed one 28-day treatment cycle without a DLT. If at least 1 of 3 patients experiences a DLT at any dose level, the cohort will be expanded to 6 patients. If $\geq 2/3$ or $\geq 2/6$ patients experience a DLT within a cohort, the MTD will be considered to have been exceeded. No additional patients will be enrolled in that cohort, and dose escalation will stop. If at least 3/3 or 5/6 patients have completed one 28-day treatment cycle at the previous dose level without a DLT, then that dose may be accepted as the MTD. At Sponsor discretion, additional patients may be enrolled into a cohort where ≤ 1 patient develops a DLT to obtain additional safety, PK, PD, and/or efficacy data.

If greater than 1/6 patients experience a DLT at DL 1, then 100 mg BID may be declared the MTD, or intermediate dose levels and/or alternative dosing schedules may be evaluated upon review of safety, pharmacodynamic, and/or pharmacokinetic data.

Each dose cohort will include a minimum of 3 evaluable patients for assessment of DLT. In order to be considered evaluable for DLT, patients must meet at least one of the following criteria:

- 1. Complete dosing through the DLT period and receive at least 75% of MS-553 intended doses during that time.
- 2. Discontinue due to DLT

During the DLT evaluation period, non-evaluable patients who discontinue treatment before DLT period is complete for reasons other than study drug-related toxicities (e.g., progressive disease, non-compliance) or do not receive at least 75% of MS-553 intended doses in the DLT period, will be replaced with additional patients enrolled at the same dose level. After a DLT is resolved or reversed to \leq Grade 1, the study drug may continue at a lower dose level at the discretion of the investigator.

A decision on dose escalation to the next dose level will be based on evaluation of the clinical safety profile, and may also include evaluation of MS-553 exposure in treated patients. After the completion of each cohort, safety and PK data (if available) will be reviewed and a decision on dose escalation will be determined by the Investigators, the Safety Review Committee, and the Sponsor.

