6.1.7. Dose Modifications and Dose Delay

Investigators should follow the guidelines described herein for the modification of MS-553 treatment. Any plan to deviate from these guidelines in view of patient safety must be

previously discussed with the study Sponsor and the medical monitor unless there is an urgent need for action.

All dose modifications should be based on the worst preceding toxicity. If study treatment is being held due to toxicity, scheduled visits and all safety assessments in Cycle 1 should continue to occur, even without dispensation of the study drug. Additional scheduled visits and assessments including all PK samplings may be adjusted according to the actual dosing schedule upon the agreement between the investigator, the study medical monitor, and the Sponsor.

Recommended modifications to dosing (not including dose-limiting toxicities in the first cycle) are described in Appendix 2A (MS-553 Recommended Dose Modifications and Delays for Toxicity).

A maximum of three dose reduction steps but not lower than 100 mg BID as a single agent will be allowed, after which the patient will be discontinued from study treatment if there is a need for further dose reduction. In the combination regimens of cohort B and C, dose reductions to not lower than 50 mg BID is allowed.

For patients who undergo dose interruptions (delays) due to toxicity, if the same toxicity returns after re-initiation of treatment, regardless of duration, the second re-initiation of study drug must resume at the next lower dose level. However, the dose of MS-553 that is restarted could be reduced if the investigator feels it prudent to re-challenge at a lower dose. Please refer to Appendix 2A for dose modification instructions.

Recommended modifications to dose and schedule for the combination treatments are outlined in Appendix 2B and 2C, and according to institutional standard of care.

If the patient requires a dose interruption of > 28 days from previous dose for either MS-553 or combination treatment, then the patient must be discontinued from study treatment. Patients who discontinue the treatment due to an adverse event or an abnormal laboratory value, even if not related to study drug, must be followed until resolution or stabilization of the event.

All dose changes or interruptions must be recorded in the dosage administration record CRF.

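### DLT-evaluability in the combination escalation cohorts B1 and C1 counts MS-553 doses only, so a patient who missed most or all partner-drug doses for non-toxicity reasons counts as DLT-free for the combination

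*Combined protocol and SAP*

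**What the plan says.** The primary objectives of Cohorts B and C (Sections 2.2.1 and 2.3.1) include finding the MTD or initial RP2D of MS-553 in combination.

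Evaluability for a patient without a DLT is stated in three places:
- Synopsis, Cohort B1: "Complete one 28-day cycle and receive at least 75% of MS-553 intended doses in Cycle 1".
- Synopsis, Cohort C1: "Complete the first four consecutive 28-day cycles and receive at least 75% of MS-553" doses over those cycles.
- Section 3.3.2, which Section 3.3.3 applies to the combination regimens: "Complete dosing through the DLT period and receive at least 75% of MS-553 intended doses during that time".

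The synopsis replacement rule uses the same yardstick: patients who "do not receive at least 75% of MS-553 doses, will be replaced with additional patients enrolled at the same dose level".

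The synopsis gives the reason for the long C1 window: "the DLT evaluation period for the triplet combination is extended to 4 cycles of therapy in order to include ramping up of the venetoclax dose". Escalation proceeds when 3/3 or 5/6 patients finish the window without a DLT.

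Two other rules bear on missed partner doses. Section 6.1.7 discontinues a patient who needs a "dose interruption of > 28 days from previous dose for either MS-553 or combination treatment". Section 3.3.5 makes it a DLT when a treatment-related event causes more than 25% of scheduled study drug doses to be withheld in the DLT period.

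**The concern.** The question for B1 and C1 is whether the combination is tolerated, but the rule deciding who may answer it checks only one component. In C1 the window was lengthened for venetoclax, and nothing requires that venetoclax be taken in it.

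Missed partner drug is foreseeable. Section 6.1.4.2 leaves the cost of acalabrutinib, venetoclax and rituximab to the insurer or the patient, so late access is plausible. Section 5.2.4.3 puts TLS risk assessment, optional restaging and, for some patients, hospital dosing around the venetoclax start.

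If such a patient has a lower DLT risk than a fully exposed one, counting that patient shifts the 3+3 decision toward escalation. The dose chosen then goes to about 50 expansion patients (B2 20, B3 10, C2 20).

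**Working it through.** **Window and dose counts.** The C1 window is 4 × 28 = 112 days = 16 weeks, which reproduces the stated length.

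| | B1 | C1 |
|---|---|---|
| Scheduled MS-553 doses (BID) | 28 × 2 = 56 | 112 × 2 = 224 |
| MS-553 doses required (75%) | 42 | 168 |
| Scheduled partner dosing | 56 acalabrutinib doses | 56 venetoclax days (Days 57–112) |
| Partner dosing required | 0 | 0 |

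Rituximab in C1 likewise has no minimum.

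**Can the 28-day interruption rule close the gap?** It runs from the previous dose.
- B1: after a single acalabrutinib dose on Day 1, the gap at Day 28 is 27 days. The rule cannot act inside the window.
- C1, venetoclax never started: there is no previous dose to count from.
- C1, venetoclax started on Day 57: doses on Days 57 and 85 alone leave gaps of 28 days, and of 27 days to Day 112. Neither exceeds 28, so 2 of 56 days satisfies the rule.

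**Can the withholding DLT close it?** Only for treatment-related events, and only if study drug includes the partner drugs, which Section 3.3.5 does not say. Access, supply and compliance gaps fall outside it.

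**Illustrated effect on 3+3.** The documents give no DLT rates. Assumed: 0.40 with the combination (range 0.30–0.50) and 0.10 without the partner (range 0.05–0.15). Formula, with patient-specific risks:

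P(pass) = P(0 of first 3) + P(1 of first 3) × P(0 of next 3)

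At 0.40 and 0.10:
- All exposed: 0.216 + 0.432 × 0.216 = 0.309.
- One unexposed, in the second three: 0.216 + 0.432 × (0.6 × 0.6 × 0.9) = 0.216 + 0.432 × 0.324 = 0.356.
- One unexposed, in the first three: 0.324 + 0.468 × 0.216 = 0.425, where 0.468 = 2 × 0.4 × 0.6 × 0.9 + 0.6 × 0.6 × 0.1.
- One in every three unexposed: 0.324 + 0.468 × 0.324 = 0.476.

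Range for one in every three:

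| Combination DLT rate | All exposed | One in three unexposed at 0.10 | At 0.15 to 0.05 |
|---|---|---|---|
| 0.30 | 0.494 | 0.629 | 0.596–0.663 |
| 0.40 | 0.309 | 0.476 | 0.447–0.504 |
| 0.50 | 0.172 | 0.332 | 0.311–0.353 |

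**The case against.** The strongest reply is that escalation is not mechanical. The Safety Review Committee must confirm each step, sees all safety and available PK data, and may expand a cohort. Table 7 schedules post-venetoclax PK samples in C1, Section 6.1.6 has combination compliance recorded, and Appendix 1C has five visits in Cycle 3, so a patient who never starts venetoclax would be hard to overlook. This stands as mitigation. However, the only exposure named in the escalation decision is that of MS-553, and a patient who meets the written rule is evaluable even if the committee notices the gap.

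Second, Section 6.1.6 speaks of study drug accountability for the combination treatments, which supports a wide reading of study drug in Section 3.3.5. On that reading, partner doses lost to treatment-related toxicity beyond 25% are already DLTs. That is why the point is confined to non-toxicity reasons.

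Third, the general wording in Section 3.3.2 about completing dosing could be read to cover all drugs. It sets no partner threshold, and the B1 and C1 criteria do not say so either.

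Fourth, in B1 acalabrutinib starts with MS-553 on Cycle 1 Day 1, so a complete failure to start is less likely there than for venetoclax. That lowers the likelihood in B1, but the wording gap is the same.

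A reader might also infer that a four-week-late venetoclax start leaves a patient unexposed. The schedule does not support that: such a patient still takes four weekly ramp steps within the window (Days 85–112, 28 of 56 scheduled days), and the stated purpose of the window is to include the ramp-up, not to secure days at full dose. With an assumed intermediate risk of 25% for such a patient, one in every three gives 0.27 + 0.45 × 0.27 = 0.39, not 0.48.

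**Conclusion.** The gap holds as a matter of wording in both B1 and C1: evaluability and dose-based replacement ignore the partner drugs, and neither the 28-day rule nor the withholding DLT covers omissions unrelated to toxicity. The direction follows whenever a patient without the partner has a lower DLT risk: the rule then leans toward escalation.

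The size is an illustration, not an estimate. It rests on assumed DLT rates, on an assumed number of unexposed patients, and on no intervention by the Safety Review Committee. At 40% and 10%, one such patient in a six-patient level moves the pass probability from 0.31 to 0.36–0.43.

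A reader might infer from the same formula that an over-toxic level would usually pass, since two unexposed patients in every three give 0.70. Nothing in the documents suggests non-exposure on that scale, so that figure should not be used to describe this trial. The point merits a correction to the protocol; it does not show that any combination dose already chosen is unsafe.

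**What to change.** In Section 3.3.2 and in the synopsis criteria for B1 and C1:
- For a patient without a DLT, require a minimum share of scheduled partner-drug doses in the DLT window in addition to 75% of MS-553. The protocol's existing 75% standard is an obvious candidate (42 of 56 acalabrutinib doses in B1, 42 of 56 venetoclax days in C1); the level is for the sponsor to set. State how rituximab is counted.
- Replace patients who miss this share for non-toxicity reasons.
- Keep patients whose partner doses were held for toxicity in the denominator and flag them for Safety Review Committee review. Without this limit the change would bring its own bias. For example, Grade 4 neutropenia shorter than the 7 days in Section 3.3.5 is not a DLT under that criterion, but Appendix 2C interrupts venetoclax for it until recovery. Replacing such a patient would remove someone who tolerated the combination poorly.
- In Section 3.3.5, state whether study drug in the 25% withholding criterion includes the partner drugs, so that it is reconciled with Section 6.1.6 and the evaluability rule.

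The cost is protocol wording and an occasional replacement patient in cohorts of about 12. In C1 each replacement can add up to 16 weeks, the length of the window.

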Relapsed after, or refractory to, progressing after at least two prior lines of therapies with the following exceptions: Patients with a 17p deletion who have already received venetoclax; or a. Patients who have TP53 mutation (prior therapy is not required) which shall b. be confirmed at screening for enrollment. or Patients with clinical and/ or molecular (e.g., BTK and/or PLCG2 mutation) c. resistance after achieving initial response to a BTK inhibitor. For patients without clinical resistance, molecular resistance (i.e., BTK and/or PLCG2 mutation) shall be confirmed at screening for enrollment. Cohort A2 (MS-553 monotherapy) Relapsed/refractory CLL/SLL patients who have: a. Failed at least two prior lines of therapies, or b. Developed clinical and/or molecular (i.e., BTK and/or PLCG2 mutation) resistance after achieving an initial response to a BTK inhibitor. For patients without clinical resistance, molecular resistance (i.e., BTK and/or PLCG2 mutation) shall be confirmed assay at screening for enrollment. Cohort A3 (MS-553 monotherapy) See Inclusion Criterion #4 below. Cohort B1, B2 (MS-553 in combination with acalabrutinib) Treatment experienced patients with no more than two prior lines of therapies, who a. Are naïve to prior BTK inhibitor treatments, and b. Are eligible for single agent BTK inhibitor. Cohort B3 (MS-553 in combination with acalabrutinib) Treatment experienced patients receiving no more than two prior lines of therapies, who: Are naïve to prior BTK Inhibitor treatments, a. b. Are eligible for single agent BTK inhibitor, and Have 17p deletion or TP53 mutation which shall be confirmed C. at screening for enrollment. (

Cohort C1, C2 (triple regimen of MS-553 + rituximab + venetoclax)

Treatment experienced patients receiving no more than 2 prior lines of treatment regimens, who:

- a. Are naïve to prior Bcl-2 inhibitor treatments, and
- b. Are eligible for venetoclax in combination with rituximab.
- 4. For inclusion in the Cohort A3, patients must meet both of the following diagnostic criteria instead of inclusion criterion #2 or #3:
 - a. Diagnosis of aggressive lymphoma, explicitly comprising Richter's Transformation of CLL/SLL to Diffuse Large B-Cell Lymphoma (DLBCL); Activated B-cell (ABC) or non-Germinal Center B-cell (GCB) DLBCL not transformed from CLL/SLL, or MCL. Other histologies may be included after discussion with and approval of the study principal investigator and Sponsor medical monitor.
 - b. Additionally, patients with MCL, or de novo ABC or non-GCB DLBCL patients must have received at least two lines of prior therapy and MCL patients must have failed at least a BTK inhibitor. Patients with Richter's transformation have no such restriction on the use of prior therapy.
- 5. WHO/ECOG performance status ≤ 2 .
- 6. Meet laboratory parameters (see Exclusion Criteria).
- 7. In the opinion of the investigator, all of the following criteria are met:
 - a. Have life expectancy \geq 2 months
 - b. Are willing to undergo all study-related evaluations and procedures, and
 - c. Have ability to understand and willingness to execute a written informed consent document.

Exclusion Criteria: Patients who meet any of the following criteria are not eligible for this study.

- 1. Current or past transformation of CLL/SLL to prolymphocytic leukemia (PLL), non-Hodgkin lymphoma, or Hodgkin lymphoma.
 - Patients being considered for inclusion in the optional expansion cohort A3 (aggressive lymphoma) are not excluded on the basis of transformed lymphoma, but must meet the definition of aggressive lymphoma outlined in the inclusion criteria for Cohort A3.
- 2. Active and uncontrolled autoimmune cytopenia(s).
- 3. Any of the following prior therapies within 14 days prior to Cycle 1 Day 1:

a. Major surgery

- b. Corticosteroids greater than 20 mg / day prednisone (or equivalent), unless used by inhalation, topical, or intra-articular routes, or unless necessary for premedication before and/or after iodinated contrast dye. Higher doses, and more prolonged courses of steroids are permitted under certain circumstances after discussion with the medical monitor and/or Sponsor including, but not limited to, the following:
 - i. Treatment of disease-related autoimmune hemolysis or autoimmune thrombocytopenia;
 - ii. Symptomatic relief of lymphadenopathy preferably after completion of Cycle 1;
 - iii. Symptomatic relief of B symptoms after completion of Cycle 1;
 - iv. Treatment of GVHD please discuss with medical monitor;
 - v. Short courses (up to 14 days) if needed for any intercurrent condition such as acute exacerbation of any non-disease-related condition (e.g., arthritis, asthma, COPD) including steroid dose modification required for adrenal insufficiency.
- c. Cytotoxic chemotherapy or biologic therapy, with the exception of BCR pathway kinase inhibitors for which only a 24-hour wash out prior to Cycle 1 Day 1 is required.
- 4. Failure to recover:
 - a. From clinically relevant toxicity to Grade 1 or less from prior chemo or radiotherapy or biologic therapy with the exception of alopecia, atrial fibrillation or hypertension that developed during treatment with a BTK inhibitor.
 - b. to Grade 2 or less for atrial fibrillation or hypertension that occurred as a consequence of treatment with a BTK inhibitor.
- 5. CNS leukemia/lymphoma including history of treated CNS disease even if the patient is asymptomatic.
- 6. Inadequate bone marrow function / hematopoietic reserve, except in the case of documented bone marrow involvement, evidenced as:
 - a. Absolute Neutrophil Count (ANC) < 1×10^9 /L
 - b. Platelet count < 30×10^9 /L
- 7. Inadequate liver or renal function as specified below:
 - Serum total bilirubin > 2 x ULN (upper limit of normal), or > 3 x ULN in case of liver involvement with CLL/SLL, or serum total bilirubin > 3 x ULN in patients with documented history of Gilbert's disease and normal direct bilirubin.

[figure not shown]
- b. AST or ALT > 2.5 x ULN, or > 5 x ULN if CLL/lymphoma is present in the liver
- c. Estimated GFR < 30 mL/min.
- 8. For Cohort B patients, active treatment with strong CYP3A inhibitors, CYP3A inducers or proton pump inhibitors, unless medication can be stopped prior to enrollment in the study.
- 9. For Cohort C patients, active treatment with strong and moderate CYP3A inhibitors, strong CYP3A inducers, or strong P-gp inhibitors, unless medication can be stopped prior to enrollment in the study.

- 12. Receiving treatment with medications that are known to be strong inducers, inhibitors or sensitive substrates of CYP3A4/5 or medications with risk for QT prolongation that cannot be discontinued prior to study entry (at least 48 hours prior to the start of Cycle 1 Day 1 dosing). For any exceptions, discussion with medical monitor and/or Sponsor is needed. Weak or moderate inhibitors may be used with caution, except as otherwise specified in Exclusion Criteria. Examples of these medications are listed in Appendix 3.
- 13. Clinically significant cardiac diseases, including any of the following:
 - a. History or presence of ventricular tachyarrhythmia
 - b. Presence of unstable/uncontrolled atrial fibrillation is exclusionary. Patients with stable atrial fibrillation (rate controlled pharmacologically) are eligible provided that they do not meet any other exclusion criteria. Patients whose atrial fibrillation occurred as a consequence of treatment with a BTK inhibitor may be eligible for the study provided that the patient is asymptomatic and on a stable dose of medication for rate control, and only after discussion with the medical monitor.
 - c. Unstable angina pectoris or acute myocardial infarction within 3 months prior to start of study drug.
 - d. NYHA functional class III or IV heart failure
 - e. Baseline QTcF interval of > 480 msec. Prior QTc prolongation due to prior medication no longer on board is not exclusionary. A family history of QTc interval prolongation by itself is not exclusionary provided that the patient's QTc is not prolonged. For those with prolonged QTc interval due to bundle branch block, patient may be eligible after documentation of a "corrected value" ≤480 msec and confirmation by cardiologist that patient is asymptomatic and that no other

cardiac conduction or cardiac abnormality is present that would pose any safety issue for the patient.

Note: As the eligibility criteria specify the QT interval corrected by the method of Fridericia (QTcF), any correction for widened QRS should be sure to include a cube-root corrected R-R interval. Please discuss/consult with a cardiologist if there are any questions.

14. History of another malignancy that in the opinion of the investigator limits survival to less than 2 years.

- 18. Known HIV positivity, or active hepatitis B or C infection with detectible viral nucleic acid in the blood.
- 19. Severe systemic infections requiring intravenous antibiotics within the two weeks prior to initiation of MS-553.
- 20. Any other life-threatening illness, medical condition, laboratory abnormalities, or therapies that in the opinion of the investigator could compromise the safety of the patient or interfere with analysis of study endpoints.
- 21. Women who are lactating or pregnant.
- 22. Women of child-bearing potential or male partners of women of child-bearing potential who will not agree to use highly effective method of contraception throughout the entire study period and for a minimum of 3 months after the last dose of study drug. Highly effective contraception methods include:
 - a. Total abstinence or
 - b. Male or female sterilization or
 - c. Combination of any two of the following:
 - i. Use of oral, injected or implanted hormonal methods of contraception
 - ii. Placement of an intrauterine device (IUD) or intrauterine system (IUS)
 - Barrier methods of contraception: condom or occlusive cap (diaphragm or cervical/vault caps) with spermicidal foam/gel/film/cream/vaginal suppository.

Women are considered post-menopausal and not of child-bearing potential if they have had 12 months of natural (spontaneous) amenorrhea with an appropriate clinical profile (age appropriate, history of vasomotor symptoms) or have had surgical bilateral oophorectomy (with or without hysterectomy) or tubal ligation at least six weeks ago. In the case of oophorectomy alone, only when the reproductive status of the woman has been confirmed by follow up hormone level assessment is she considered not of childbearing potential.

Women of child-bearing potential who will not agree to the following are ineligible for the study:

- Refrain from breastfeeding and donating oocytes or blood during the course of the study and for 3 months after the last dose of study drug, and
- Ongoing pregnancy testing during the course of the study and at the end of treatment visit.
- 23. Men who will not agree to the following are ineligible for the study:
 - Refrain from donation or blood during the course of the study and for 3 months after the last dose of study drug, **and**
 - Completely abstain from sexual contact, or must always use a latex or synthetic condom during any sexual contact until 3 months after the last dose of study drug, or have prior documentation of surgical sterilization.

Investigational product, dosage and mode of administration in all Cohorts in A, B, C: MS-553 is administered orally, twice daily, in 28-day cycles. Dose levels include 100, 150, 200, 225, 250 and 300 mg.

Cohort B: Standard of care acalabrutinib will be administered according to the Full Prescribing Information in combination with MS-553.

Cohort C: Standard of care rituximab will be administered beginning in Cycle 1, according to the Full Prescribing Information, in combination with MS-553 for two cycles. Beginning in Cycle 3, venetoclax will be started and the dose escalated from 20 mg to 400 mg over five (5) weeks in combination with rituximab and MS-553.

Duration of treatment: Patients may continue receiving study drug provided they continue to tolerate the drug, have no evidence of progression, do not meet any of the criteria for discontinuation, and the patients' participation in the study has not ended. The anticipated median treatment duration is unknown.

Reference therapy, dosage and mode of administration:

Not applicable.

Statistical methods:

Summary statistics will be provided for all endpoints. Statistics will be reported according to intention-to-treat (ITT), per-protocol, and per-dose-level. The safety summary statistics will include any patient who received at least one dose of study drug.

Patient characteristics will be described and summarized for each dose level and in total.

Because disease-relevant pharmacodynamics biomarkers are not yet established, and some limited toxicity and pharmacokinetic data in healthy subjects exists, dose escalation will be guided by toxicity.

There is no formal hypothesis to be tested in this study; therefore, no predefined sample size calculation has been made for the efficacy or exploratory endpoints.

The protocol details dose modifications (i.e., reductions, interruptions) that may be warranted as a consequence of drug-related toxicities. At a starting dose level of 100 mg BID (Dose Level 0), no dose reduction is anticipated as monotherapy. If unacceptable toxicity presents during Cycle 1 at Dose Level 0 then the patient will be instructed to discontinue treatment with MS-553. If a patient experiences potential drug-related toxicity, the appropriate dose modification may be implemented until the toxicity has adequately resolved or improved to Grade 1. If unacceptable toxicity presents, then the patient will be instructed to discontinue treatment with MS-553.

Formal stopping criteria are specified in Section 7.13. Since the study is unblinded, the Precision Oncology medical monitor, the Safety Review Committee, the relevant MS-553-103 Investigator(s), and the Sponsor will closely review available safety and PK data on an ongoing basis throughout the dose escalation and dose expansion segments of the open-label study.

TABLE OF CONTENTS, LIST OF TABLES, AND LIST OF FIGURES

TABLE OF CONTENTS

SYNOPSIS		4
TABLE OF C	CONTENTS, LIST OF TABLES, AND LIST OF FIGURES	8
LIST OF AB	BREVIATIONS AND DEFINITIONS OF TERMS	4
1.	INTRODUCTION	7
1.1.	Chronic Lymphocytic Leukemia	7
1.1.1.	B Cell Receptor (BCR) Signaling Inhibitors	7
1.1.2.	Protein Kinase C and PKC-β	8
